7.4.2.4. End of Treatment Visit for the Open-Label Extension Phase

Patients are to complete an EOT Visit after they complete the study; the evaluations of safety and effectiveness to be performed at the EOT Visit in the OLE Phase are the same as those listed for Visit 10 (Section 7.4.2.1).

7.4.3. Early Termination Visit for Open-Label Extension Phase

Every effort should be made to perform the ET evaluations for patients who terminate early from the OLE Phase of the study. At the ET Visit, the reason for early termination must be recorded. The evaluations of safety and effectiveness to be performed at the ET visit are the same as those listed for Visit 10 (Section 7.4.2.1).

7.5. Safety Follow-Up Telephone Calls

Patients in the Double-Blind Treatment Phase who do not enter the optional OLE Phase will receive a TC from the study site 15 days (±3 days) and 30 days (+3 days) after their final dose of study drug to assess for AEs (including inquiries regarding signs and symptoms of arrhythmia, any other cardiac manifestations [e.g., syncope], and psychiatric events [e.g., suicidality, compulsive behavior, anxiety]) and use of concomitant medications and to complete the C-SSRS and ADAMs.

Patients (and/or their caregivers) in the OLE Phase will receive a TC from the study site 15 days (±3 days) and 30 days (+3 days) after their final dose of study drug to assess for AEs (including inquiries regarding signs and symptoms of arrhythmia, any other cardiac manifestations [e.g., syncope], and psychiatric events [e.g., suicidality, compulsive behavior, anxiety]) and use of concomitant medications and to complete the ADAMS.

An on-site unscheduled study visit will be requested for any patient reporting signs and symptoms of arrhythmia or cardiac manifestations, and/or a psychiatric event at either of the two Safety Follow-up TCs (Section 7.6).

7.6. Unscheduled Visits and Assessments

Unscheduled visits and assessments in the Double-Blind Treatment Phase and OLE Phase of the study may be conducted by telephone or at an on-site study visit and should be performed if clinically indicated in the opinion of the Investigator.

At minimum, the following assessments are to be performed at an unscheduled on-site study visit:

- Abbreviated physical examination
- Body weight
- Height
- Vital signs
- Review of AEs
- Review of concomitant medications
- Review study drug compliance/accountability (Section 5.5 and Section 5.6)

Other assessments (e.g., 12-lead ECGs, clinical laboratory tests, urine pregnancy test, Very Young Child/Cognitively Impaired-Since Last Contact C-SSRS, ADAMS, ABC-C) can be completed based on the reason for the unscheduled visit and at the Investigator's discretion.

At a minimum, AEs, concomitant medication use, and study drug accountability/compliance should be assessed during unscheduled TCs. Other assessments (e.g., Very Young Child/Cognitively Impaired-Since Last Contact C-SSRS, ADAMS, ABC-C) can be completed based on the reason for the unscheduled TC and at the Investigator's discretion.

8. SAFETY MONITORING AND REPORTING

Investigators are responsible for the detection and documentation of events that meet the definition of an AE, SAE, suspected adverse reaction, serious suspected adverse reaction, or unanticipated problem, as provided in this protocol.

Investigators must review the WAKIX (pitolisant) IB to be knowledgeable about the study drug and aware of its safety profile. Investigators will also be versed in the latest standard of care guidelines.

8.1. Definition of Safety Parameters

8.1.1. Definition of an Adverse Event

An AE is defined as any untoward medical occurrence associated with the use of a drug in humans, whether or not considered drug related.

An AE may be any unfavorable or unintended sign (including an abnormal laboratory finding), symptom, or disease temporally associated with the use of a study drug, whether or not considered causally associated with the use of the study drug. Any abnormal physical examination findings, laboratory value, vital sign result, or ECG finding that is deemed clinically significant by the Investigator, regardless of causal relationship, must be reported as an AE. A clinical diagnosis, rather than the changes in laboratory analyte or other assessment, should be recorded (e.g., anemia rather than low hemoglobin value).

Examples of AEs include:

- Significant or unexpected worsening or exacerbation of the condition or indication under study.
- Exacerbation of a chronic or intermittent pre-existing condition, including either an increase in frequency or intensity of the condition (e.g., abnormal physical examination finding related to the condition).
- Signs, symptoms, or clinical sequelae of a suspected overdose of the study drug or a concurrent medication (overdose per se should not be reported as an AE or SAE, unless nonserious or serious sequelae occur).
- A diagnosis related to any clinically significant abnormal laboratory test result.
- Any laboratory abnormality not associated with a diagnosis or symptom requiring further diagnostic investigation.

The following examples would not be considered AEs:

- Medical or surgical procedure (e.g., endoscopy, appendectomy), although the condition that leads to the procedure would be considered an AE.
- Anticipated day-to-day fluctuations of pre-existing disease(s) or condition(s) (including laboratory values) present or detected at the start of the study that do not worsen during the study.

• The disease or disorder being studied, or expected progression, signs, or symptoms of the disease or disorder being studied, unless they become more severe or occur with a greater frequency than expected for the patient's condition.

8.1.2. Definition of a Serious Adverse Event

An AE or suspected adverse reaction is considered "serious" if, in the view of either the Investigator or the Sponsor, it results in any of the following outcomes:

- Death
- A life-threatening AE (i.e., presented an immediate risk of death from the event as it occurred; this criterion is not intended to include an AE that, had it occurred in a more severe form, might have caused death)
- Inpatient hospitalization or prolongation of existing hospitalization
- A persistent or significant incapacity or substantial disruption of the ability to conduct normal activities of daily living
- A congenital anomaly/birth defect
- Important medical events that may not result in death, be life-threatening, or require hospitalization may be considered serious when, based upon appropriate medical judgment, they may jeopardize the patient and may require medical or surgical intervention to prevent one of the outcomes listed in this definition. Examples of such medical events include allergic bronchospasm requiring intensive treatment in an emergency room or at home, blood dyscrasias or convulsions that do not result in inpatient hospitalization, or the development of drug dependency or drug abuse.

The following events do not meet the definition of an SAE:

- Hospitalization for elective treatment of a pre-existing condition that does not worsen from baseline
- Hospitalization for a standard procedure for study drug administration and routine monitoring of the studied indication not associated with any deterioration in condition
- Social or convenience admission to a hospital
- Prolongation of a hospitalization for social or convenience reasons not associated with the occurrence of an AE
- Hospitalization or an emergency room visit that lasts less than 24 hours that does not meet the criteria of an important medical or a life-threatening event

8.1.3. Definition of a Suspected Adverse Reaction

A suspected adverse reaction is defined as any AE for which there is a reasonable possibility that the AE was caused by the study drug.

8.1.4. Definition of a Serious Suspected Adverse Reaction

A serious suspected adverse reaction is any suspected adverse reaction that is determined to be serious, based on the definition of an SAE described in Section 8.1.2.

8.1.5. Definition of Unanticipated Problems

Unanticipated problems are incidents, experiences, or outcomes that meet all of the following criteria:

- Unexpected in terms of nature, severity, or frequency given (a) the research procedures that are described in the protocol-related documents, such as the research protocol and informed consent document approved by the Ethics Committee (EC; includes Institutional Review Boards [IRBs], Independent ECs, and Research Ethics Boards) and (b) the characteristics of the participant population being studied
- Related or possibly related to participation in the research ("possibly related" means there is a reasonable possibility that the incident, experience, or outcome may have been caused by the procedures involved in the research)
- Suggest that the research places patients or others at a greater risk of harm (including physical, psychological, economic, or social harm) than was previously known or recognized

8.2. Classification of Adverse Events

8.2.1. Severity of Adverse Events

The Investigator will assess the severity of each AE based on his/her clinical judgment using one of the following categories:

- **Mild:** Usually transient and may require only minimal treatment or therapeutic intervention. The event does not generally interfere with usual activities of daily living.
- **Moderate:** Usually alleviated with additional specific therapeutic intervention. The event interferes with usual activities of daily living, causing discomfort but poses no significant or permanent risk of harm to the patient.
- Severe: Interrupts usual activities of daily living, or significantly affects clinical status, or may require intensive therapeutic intervention.

8.2.2. Relationship to Study Drug

The Investigator will assess the relationship (i.e., causality) of each AE to study drug based on his/her clinical judgment. The Investigator's assessment of the relationship of an AE to study drug is part of the documentation process, but it is not a factor in determining what is or is not reported in the study. If there is any doubt as to whether a clinical observation is an AE, the event should be reported. All AEs must have their relationship to study drug assessed. The Sponsor's assessment of relationship may differ from the Investigator's assessment.

Relationship to study drug will be assessed according to the following guidelines:

- **Not related:** There is not a temporal relationship to study medication administration, or the AE is clearly and incontrovertibly due only to progress of the underlying disease or to extraneous causes.
- Unlikely related: There is little or no chance that the study treatment caused the reported AE; the event is most likely because of another competing cause, including concomitant illnesses, progression or expression of the disease state, or a reaction to a concomitant medication.
- **Possibly related:** The association of the AE with study treatment is unknown; however, the AE is not reasonably attributed to any other condition.
- **Probably related:** A reasonable temporal association exists between the AE and study treatment, and based on the Investigator's clinical experience, there is no other obvious competing cause. The event responds to withdrawal of the study medication (positive dechallenge) and rechallenge with administration of the study medication is ambiguous or not done.
- **Definitely related:** There is a reasonable causal relationship between study treatment and the AE; the event responds to withdrawal of the study medication (positive dechallenge) and recurs with rechallenge by administration of the study medication.

For initially reporting SAEs, even in situations in which minimal information is available, it is important that for every event the Investigator make an assessment of causality. The causality assessment is one of the criteria used when determining regulatory reporting requirements. The Investigator may change his or her opinion of causality based on follow-up information and amend the SAE information accordingly in the eCRF or the SAE reporting form, as applicable.

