12.6.1 Adverse Events

An AE is defined as any untoward medical occurrence associated with the use of a drug in humans, whether or not considered drug related.

A TEAE is defined as any event not present before exposure to study drug or any event already present that worsens in intensity or frequency after exposure and up to 30 days after the last dose of study drug. For the OLE Phase, any AE starting on or after the first dose of OLE treatment will be considered treatment emergent.

A serious AE (SAE) is defined as any AE that results in any of the following outcomes: death, is life-threatening, results in inpatient hospitalization or prolongation of existing hospitalization, results in a persistent or significant incapacity or substantial disruption of the ability to conduct normal activities of daily living, or is a congenital anomaly/birth defect. Important medical events that may not result in death, be life-threatening, or require hospitalization may be considered SAEs when, based upon appropriate medical judgment, they may jeopardize the patient and may require medical or surgical intervention to prevent one of the outcomes listed in this definition.

The AE's relationship to study treatment will be evaluated by the investigator. The following relationships will be collected in eCRF: definitely related, probably related, possibly related,

unlikely related, or not related. The AEs that are evaluated as definitely, probably, or possibly related (or with missing relationship) will be considered treatment-related AEs for summary purposes.

The severity of AEs will be classified by the investigator as mild, moderate, or severe. If the severity is missing, the AE will be assumed to be severe.

An overall AE summary will be generated presenting the frequency and percentage of patients and the number of AEs for the following categories. This overall summary will also be provided for each age groups (6 to <12 years; 12 to <18 years and 18 years or older) for the Double-Blind Treatment Phase. The same summary may be repeated for the OLE Phase.

- Any TEAE
- Any treatment-related TEAE
- Any severe TEAE
- Any treatment-related severe TEAE
- Any serious TEAE
- Any treatment-related serious TEAE
- Any TEAE leading to study discontinuation
- Any TEAE leading to discontinuation of investigational product (IP)
- Any TEAE leading to discontinuation of IP and leading to study discontinuation
- Any TEAE leading to interruption of IP
- Any TEAE leading to death

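### Protocol 8.2.2 defines Possibly related more narrowly than the protocol's own reasonable-possibility standard, so adverse events with both a plausible drug cause and a plausible other cause risk being rated unrelated

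*Protocol*

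**What the plan says.** Protocol 8.2.2 gives the investigator five causality categories and introduces them thus: "Relationship to study drug will be assessed according to the following guidelines". The conditions that matter here are:

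- *Not related*: no temporal relationship, or "the AE is clearly and incontrovertibly due only to progress of the underlying disease or to extraneous causes".
- *Unlikely related* sets a test in two parts: "There is little or no chance that the study treatment caused the reported AE; the event is most likely because of another competing cause".
- *Possibly related* is worded thus: "The association of the AE with study treatment is unknown; however, the AE is not reasonably attributed to any other condition".
- *Probably related*: it needs a reasonable temporal association, a positive dechallenge, rechallenge ambiguous or not done, and "there is no other obvious competing cause".
- *Definitely related*: a reasonable causal relationship, where "the event responds to withdrawal of the study medication (positive dechallenge) and recurs with rechallenge by administration of the study medication".

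The section requires a relationship assessment for every AE.

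Protocol 8.1.3 defines a suspected adverse reaction as "any AE for which there is a reasonable possibility that the AE was caused by the study drug". Protocol 8.1.5 likewise explains a possible relationship to research participation as a reasonable possibility of causation. Neither excludes an event because another cause is also plausible.

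Two rules depend on the rating. SAP 12.6.1 states: "The AEs that are evaluated as definitely, probably, or possibly related (or with missing relationship) will be considered treatment-related AEs for summary purposes". Protocol 8.3.1 covers patients who received double-blind study drug and did not enter the OLE. For an SAE that comes to light after their participation, it asks for a report if the investigator considers the event possibly related.

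**The concern.** The protocol applies two tests to one idea. Under 8.1.3 and 8.1.5, a reasonable possibility of drug cause is enough. Under 8.2.2, the lowest category that counts as related is closed once another condition reasonably explains the event.

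Events with two plausible causes are foreseeable in this trial. Protocol 1.1 describes early waking in Prader-Willi syndrome (PWS) and links it to anxiety, compulsive behavior and depression. Protocol 1.4 lists insomnia (8.5%) among the most frequent events on pitolisant, and says that most of those frequent events were considered treatment-related. Protocol 7.5 asks specifically about suicidality, compulsive behavior and anxiety at the safety follow-up calls.

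Two outputs are exposed. The first is the set of treatment-related summaries in SAP 12.6.1: related, severe related and serious related events, some of them by age group. The second is SAE reporting after participation under Protocol 8.3.1, where a literal reading could mean that no report is made. The related tables also carry more interpretive weight in the OLE, which has no concurrent placebo group.

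**Working it through.** The plan states no figure to reproduce, so the check sets the definitions against one type of event.

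**Test event.** The AE follows dosing in time. There is a reasonable possibility that study drug caused it. Another condition also plausibly explains it, but is neither the only cause nor clearly the most likely one.

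**Each category in turn (Protocol 8.2.2).**

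1. *Not related* fails. There is a temporal relationship, and the event is not clearly due only to something else.
2. *Unlikely related* fails. A reasonable possibility is more than little or no chance, and the other cause is not clearly the most likely.
3. *Possibly related* fails. Another condition reasonably explains the event.
4. *Probably related* fails, taking the plausible alternative as an obvious competing cause. It also needs a positive dechallenge.
5. *Definitely related* has no competing-cause exclusion, but needs positive dechallenge and positive rechallenge.

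**Result by available information.**

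- No dechallenge information: no category fits.
- Positive dechallenge, no rechallenge: no category fits.
- Positive dechallenge and positive rechallenge: only *Definitely related* fits.

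Step 4 has one soft edge. If the alternative is plausible but not obvious, an investigator with a positive dechallenge could argue for *Probably related*, although the weaker category *Possibly related* would stay closed.

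**The same event under the other sections.** It meets 8.1.3 directly, and it meets the reasonable-possibility meaning in 8.1.5. So it can be a suspected adverse reaction and yet not be possibly related under 8.2.2.

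**Effect on the tables.** Let m be the share of drug-plausible AEs that are mixed-cause, and u the share of those rated *Unlikely related* or *Not related*. Under SAP 12.6.1, the proportional shortfall in the treatment-related count is m × u. The documents give neither m nor u, so these values are assumptions for illustration only:

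- m = 30%, u = 0%: 0.30 × 0 = 0%
- m = 30%, u = 50%: 0.30 × 0.50 = 15%
- m = 50%, u = 100%: 0.50 × 1.00 = 50%

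The range starts at zero, so the formula shows the mechanism and does not estimate its size.

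**The case against.** The strongest reply is that the text does not force a low rating. The categories are guidelines applied with clinical judgment. The test event fails *Unlikely related* at least as clearly as it fails *Possibly related*, so an investigator facing the gap may well choose the latter. This stands. A reader might infer that treatment-related AEs are in fact undercounted; the documents support a risk in that direction, not a result. The SAP rule that a missing relationship counts as related helps little, because Protocol 8.2.2 requires every AE to be assessed.

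A second reply concerns PWS. A reader might infer that anxiety, irritability and sleep problems nearly always have a disease explanation. The documents do not say so. Protocol 8.1.1 does not count expected symptoms of the disorder as AEs unless they become more severe or frequent than expected for the patient, and 6.5.6 records only new or worsening anxiety. Events that reach causality assessment have therefore already exceeded the expected background. This weakens the disease explanation without removing it, since worsening can itself come from the disease.

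Third, much of the safety evidence does not pass through causality. SAP 12.6.1 tabulates all treatment-emergent AEs, and all AEs and SAEs, by system organ class and preferred term. SAP 12.6.8 summarizes the anxiety and mood scale separately. Protocol 8.4.1 requires SAEs in the study to be reported within 24 hours whatever their relationship. Protocol 8.2.2 says that causality does not decide what is reported in the study and that the sponsor's assessment may differ from the investigator's. Protocol 8.4.3 frames onward reporting around serious suspected adverse reactions, which 8.1.4 and 8.1.3 define by reasonable possibility. All of this stands and limits the scope. It does not cover post-participation SAEs under 8.3.1.

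Finally, raters were blinded in the Double-Blind Treatment Phase, so the wording applied alike in every arm. Protocol 1.3.2 describes that phase as completed, so rewording cannot change its tables. Both points are correct. The wording remains in use for the OLE and for late SAEs.

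**Conclusion.** The wording conflict is real and rests on the text alone: 8.2.2 closes *Possibly related* to events that 8.1.3 and 8.1.5 would accept. Short of positive dechallenge and rechallenge, a mixed-cause event has no fitting category, on the assumption that a plausible alternative counts as an obvious competing cause. To say that no category can ever apply would go too far, because *Definitely related* remains open.

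Where the text steers the rating, it steers away from related. The consequence is a risk of undercount in the treatment-related tables and a risk that a post-participation SAE goes unreported. The second risk assumes that 8.3.1 is read with the 8.2.2 meaning; 8.3.1 does not say which meaning applies.

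The size is unknown. A reader might attach a figure, for example that 20 drug-plausible events would appear as 14 (20 × 0.7) or 6 (20 × 0.3) if 30% or 70% were mixed-cause. The documents supply neither the 20 nor the shares, and the sum also needs every mixed-cause event to be rated *Unlikely related* or *Not related*. If none were, the shortfall would be zero. This is a low-priority clarification with a limited reach.

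**What to change.** Reword *Possibly related* in Protocol 8.2.2 to say that there is a reasonable possibility that study drug caused or contributed to the event, even if another cause is also plausible. This agrees with 8.1.3 and 8.1.5. Update the case report form guidance to match.

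Apply the wording to ongoing and future OLE events and to SAEs assessed under 8.3.1. Keep the SAP 12.6.1 grouping as it is. Footnote the OLE treatment-related tables with the date of the change.

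The cost is one protocol sentence, matching guidance and a footnote. The downside is that ratings before and after the change rest on different wording within the same OLE tables, and the related count may rise for that reason alone.
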